
9.2. Experimental approaches and data analysis

Bioinformatic pathway enrichment analysis of outlier gene expression amongst all progressors will be used to identify common immune correlates of risk of progression to active TB at the systems level. To complement this approach, we will also reduce the dimensions of data in the TST transcriptome of all non-progressors, from individual genes into co-correlated clusters as a surrogate for immune networks³⁸. We will compare the expression of each cluster to identify statistically significant differences between progressors and non-progressors. We will then undertake pathway analysis of each differentially expressed cluster to identify the immune pathways that may influence risk of progression to active TB. Data from participants in the cross-sectional study, and those in the longitudinal study who withdraw from the study or are lost to follow up before completing 2 years follow up will be included by identifying any progressors amongst these groups by linkage to national TB surveillance records, held at Public Health England.

All 1000 participants undergoing TST transcriptional profiling will be genotyped for >1.7 million genome wide SNPs using the Illumina Infinium Multi-Ethnic Global-8 array, with additional imputation of >4 million SNPs to allow fine mapping of associations. Statistically significant SNP associations with quantitative variation in the TST transcriptome will be identified as previously described⁵⁷. Iterative eQTL analyses will be performed in year 3 after the first 400 recruits, in year 4 after 750 recruits and in year 5, using data from all 1000 individuals. In addition, we will assess whether any eQTLs are associated with immune response variation that correlate with progression to active TB, thereby identifying potential genotypic susceptibility loci via their association with a functional impact on anti-Mtb immune responses. Where possible, we will assess whether the eQTLs identified in the present study represent significant susceptibility loci for active TB using a targeted (statistically more powerful) analysis approach to re-examine previously published GWAS data. In order to make maximum use of the novel data, we will also identify eQTLs which coincide with loci associated with any phenotypic/disease traits in GWAS catalogues (www.genome.gov/gwastudies/), thereby offering novel mechanistic insights into the associations.

For in vitro mechanistic studies participants will be selected for recall by genotype (5-10 per group) to obtain peripheral blood T cells, monocytes and monocyte derived macrophages (MDM). SNP genotypes will be selected, which are associated with variations in TST response that do not correlate with IFN γ and are implicated in macrophage control of Mtb growth. We will prioritise the most tractable responses involved in cell-mediated Mtb killing mechanisms, and pathways that may affect macrophage viability. Selected cell types will be stimulated with live Mtb or Mtb-derived antigens to validate the eQTL associations by quantitative PCR and to establish the cell-type specificity of these associations. Where eQTL data suggest novel molecular interactions, we will test the predicted interaction in cells from subjects with the relevant genotypes, using lentiviral vectors to overexpress specific genes or small molecule and antibody blocking reagents as appropriate. To complement this approach, we will use CRISPR editing to reproduce genetic variants of interest in model cell lines. Finally, we will assess bacterial growth in MDM cultures, using flow cytometric quantitation of intra and extracellular Mtb. We will test Mtb growth in MDM cultures \pm selected T cell subtypes using cells from subjects with targeted genotypes.

10. Patient and public involvement (PPI)

All project staff will undergo UCL training in Public Engagement (www.ucl.ac.uk/publicengagement/training). We will take advantage of an established lay patient panel within the UCLH/UCL Biomedical Research Centre to preview and feedback on all patient information sheets and recruitment strategies. We will liaise with the UCL Public Engagement Unit (www.ucl.ac.uk/publicengagement) to describe our research to the general public and patients. We will specifically target those attending TB clinical services and migrant communities involved in the new migrant screening programme in collaboration with Public Health England, ensuring that information is presented in the range of appropriate languages. To do so, we will offer annual educational meetings for interested groups to provide information on research developments in tuberculosis and address their questions. We will optimise the value of these events using established UCL toolkits for planning and evaluation (www.ucl.ac.uk/publicengagement/evaluation/toolkits). In addition, we will take advantage of UCL resources such as the iTunes online lecture facility to broadcast seminars and lectures to a varied audience. For valuable research findings that may be of interest to the wider public including patient communities, commercial clinical services or government policy makers, we will liaise with the UCL Media Office at the time of publication to maximize opportunities for media coverage and ensure timely press releases. In line with Wellcome Trust open access policies, we will make all scientific publications derived from this project freely available by submission to Pubmed Central and the UCL Research Publications Service at the time of publication.

11. Sample management

All samples will be collected from patients in accordance with the patient consent form and patient information sheet and shall include all tissue samples or other biological materials and any derivatives, portions, progeny or improvements as well as all patient information and documentation supplied in relation to them. Samples will be processed, stored and disposed in accordance with all applicable legal and regulatory requirements, including the Human Tissue Act 2004 and any amendments thereafter.

All research samples will be labelled with the UIN at the point of collection. All research sample collection, transportation storage and processing will be performed by designated staff under the supervision of the Chief Investigator. Designated project staff will transport research samples (by road or rail in UN approved category B triple layered packaging) from the TB clinics on the day of collection to designated secure restricted access laboratories within the UCL Division of Infection and Immunity for storage or processing by designated laboratory staff. The collection, transfer, storage location and processing events related to each research sample will be recorded in a password protected electronic sample log. Any transfer of samples to other UK or non-UK research institutions, for additional analyses related to the present study will be subject to a material transfer agreement in which the new user will be responsible for restricting use of the data to agreed purposes, maintenance of confidentiality and data security, reporting publications and other outputs to the Chief Investigator of this study and restricting onward transfer of samples to a third party.

12. Data management

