The limitations in our understanding of immune protection against Mtb are a fundamental hurdle to identifying an individual's risk of active disease, and to harnessing the immune system to prevent or treat Mtb infection. On health economic grounds, systematic programs aim to prevent active TB by drug treatment of LTBI, 90% of whom do not need treatment because they will never develop disease^{10,11}. There has been no improvement on the modest efficacy of BCG vaccination¹², and treatment of Mtb infection requires prolonged antimicrobial drugs, increasingly compromised by Mtb drug resistance¹³. Greater understanding of the immune mechanisms that determine the clinical outcome of Mtb infection is a global research priority. These will allow us to target preventative measures at those with the highest risk of active disease. In addition, they will focus attention on immune responses that could be modulated to enhance vaccine efficacy, and to develop host directed therapies in order to reduce the duration of antimicrobial treatment for TB or to mitigate against increasing drug resistance¹⁴⁻¹⁷.

2. Background and rationale

TB disease arises from stochasticity in multivariate immune responses such that variation of any one of many components can tip the balance towards immunological protection or pathogenesis. Genome-wide transcriptional profiling of biopsies from the site of tuberculin skin test (TST) provides comprehensive molecular and systems level assessments of in vivo human immune responses to a standardised mycobacterial challenge, at the site of host-pathogen interactions^{20,21}. This approach allows quantitation of cell-type specific recruitment, Mtb specific innate immune responses and the biological activity of specific cytokines in response to the TST^{20,22,23}, and has been shown to represent variations in molecular pathology at the site of active disease in human TB²⁰.

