Transcriptional profiling of TST biopsies in LTBI patients with longitudinal follow up to identify immune response correlates of subsequent progression to active TB. This approach necessitates the ability to exclude active TB in patients at the time of TST challenge, to safely defer LTBI treatment, and to accurately identify individuals progressing to active TB before the onset of clinical disease. Blood transcriptomic biomarkers achieve these aims. They have been shown to accurately discriminate active pulmonary and extrapulmonary TB from LTBI or other infectious diseases²⁴. Blood transcriptomic changes can also predate diagnosis of active disease²⁵. Unpublished data has also shown that blood transcriptional signatures can identify patients who develop symptomatic active TB within 3 months, with positive and negative predictive values of 0.99-1 assuming cumulative 5% pre-test probability of progression to active disease in cohorts of TB contacts^{10,26}.

Twin studies indicate that the risk of active TB has a host genetic component. Candidate gene association studies focussing on innate immune responses have reported putative TB susceptibility loci⁴⁰⁻⁴⁹. Given the complexity of integrated innate and adaptive cell-mediated immunological systems, these studies do not offer the comprehensive approach required to identify the constellation of genetic polymorphisms that may affect TB risk. Conventional genome-wide association studies (GWAS) of active TB have not replicated the findings of candidate gene studies and generally lacked sufficient power⁵⁰⁻⁵⁵. Expression quantitative trait loci (eQTL) studies, in which genome-wide single nucleotide polymorphisms (SNPs) are associated with quantitative differences in transcriptional responses to a stimulus offer substantially greater power to identify the genetic correlates of variation in immune responses⁵⁶⁻⁵⁹. They also provide the fundamental advantage of directly

identifying the functional impact of genetic polymorphisms on both specific molecules and molecular pathways. An eQTL study of TST transcriptional responses offer an important opportunity to identify the genetic correlates of variation in anti-Mtb immune responses.

3. Objectives

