The longitudinal study will recruit individuals with LTBI from the existing UK contact screening program^{11,27}. The additional individuals for the cross-sectional study will be recruited from the Public Health New migrant screening program referrals to LTBI clinics. Clinical staff at each participating site (Appendix 1) will introduce potentially eligible individuals (Section 7) to the study team, who will seek to obtain informed written consent (see Section 6). The study schedule for participants who give consent is summarised in Appendix 2. They will undergo a chest radiograph (provided by the routine NHS Trust clinical service) and screening blood tests (Appendix 3) and, followed by one tuberculin skin test in each arm. One TST site will be biopsied at 48 hours and the second TST site will be biopsied at seven days (Appendix 4). All blood tests, chest radiography, TSTs and biopsies will be performed within the TB clinic the participant was recruited from.

Participants who have a positive blood transcriptional biomarker will then enter the LTBI treatment sub-study. In the absence of clinical evidence of active TB, they will be offered LTBI therapy as part of their usual NHS care, and asked to attend appointments after 4, 8, 12 and 24 weeks for clinical review and repeat blood sampling (the 4, 8 and 12 week time points are aligned with those required in routine clinical care for monitoring). Adherence to LTBI therapy will be measured by self-report questionnaire, pill counts, urine testing and/or medication boxes, depending on local site availability and practice.

Participants with a negative blood transcriptional biomarker and who meet the eligibility criteria for the longitudinal study will be asked to attend follow up clinic appointments with the study team at three monthly intervals for two years. These additional appointments will take place at the TB clinic the participant was recruited from. At each appointment they will complete a questionnaire (Appendix 5), undergo blood sampling

and a chest radiograph. Participants can withdraw at any time without giving a reason. Participants will also be consented for recall by selected genotype or phenotype to obtain additional peripheral blood samples within the five-year lifetime of this study for in vitro mechanistic studies (see secondary objectives).

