Participants who request to withdraw from the study or are lost to follow up will be referred back to the routine clinical service by the study team. Participants who develop a positive blood transcriptional biomarker at any point during longitudinal follow-up will then enter the LTBI treatment sub-study. Participants who develop a positive blood transcriptional biomarker or reach a study end point (Appendix 6) as a surrogate for progressive TB before 2 years, will be identified as progressors. Participants who complete 2 years follow up will be identified as non-progressors. Progressors and non-progressors will undergo routine clinical assessments to evaluate the need for any TB treatment when their participation in the study ends.

6. Recruitment and consent

Potential participants who meet the eligibility criteria will be identified by the routine tuberculosis clinical service and introduced to the study team. The study team will describe the study to these individuals, provide them with the participant information sheet, and answer their questions, in person, by telephone, by post or by email according to the participant's preferences. After at least 24 hours to consider this information, the study team will invite those who agree to participate to provide written informed consent.

For non-English speakers the study team will communicate with telephone translation services and provide translations of the participant information sheet and consent form. The original signed consent form will be filed in the study master file and a copy will be provided to the participant. All participants who are referred to the study team will be entered into a screening log with a record of their eligibility criteria, their decision to participate or reasons for declining to participate as appropriate.

7. Eligibility criteria

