7.2. Exclusion Criteria

- Age <18 or >60 years
- Unable to give written consent
- Clinical or radiographic features of active tuberculosis
- HIV-1 infection
- Active hepatitis B or C infection
- Pregnancy
- History of autoimmune disease
- History of skin disease
- History of malignancy
- Immunomodulatory drugs (Appendix 6)
- History of allergy to local anaesthetics
- History of keloid scarring

8. Clinical governance and indemnity

The risks for participants in the present study are summarised in Appendix 8.

Participants' General Practitioners will be notified of their patient's involvement in this study, subject to written informed consent by the patient.

All participants will be contacted 1 week after their final visit to check that the TST biopsy wounds have healed as expected. Where necessary, participants will be offered a further appointment for clinical review of the biopsy sites and to instigate appropriate clinical management under the supervision of the Chief Investigator.

Any participants who develop evidence of active tuberculosis will be referred for urgent review by routine clinical TB services.

All adverse events will be recorded as described in Appendix 9. All complaints and adverse events will be reported immediately to the sponsor by email ([contact]) and using the on line incident reporting form (<https://opinio.ucl.ac.uk/s?s=17671>). If the adverse event takes place within a UCLH Trust site, the event will be reported through the Trust incident reporting system (Datix). Annual progress reports will be submitted to the Research Ethics Committee.

University College London holds insurance against claims from participants for harm caused by their participation in this clinical study. Participants may be able to claim compensation if they can prove that UCL has been negligent. However, if this clinical study is being carried out in a hospital, the hospital continues to have a duty of care to the participant of the clinical study. University College London does not accept liability for any breach in the hospital's duty of care, or any negligence on the part of hospital employees. This applies whether the hospital is an NHS Trust or otherwise.

9. Statistical methods

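### All progressors are pooled whatever the interval from TST to conversion, so a trait confined to month-3 converters cannot be told apart from a response to early disease

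*Protocol*

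**What the plan says.** Section 2 (Background and rationale) sets the requirement: "This approach necessitates the ability to exclude active TB in patients at the time of TST challenge". It says blood transcriptomic biomarkers meet it. The performance it then gives is that "blood transcriptional signatures can identify patients who develop symptomatic active TB within 3 months". The accuracy attached to this claim, from unpublished data, is stated as "positive and negative predictive values of 0.99-1 assuming cumulative 5% pre-test probability of progression to active disease". The same section also says of TST profiling that it "has been shown to represent variations in molecular pathology at the site of active disease in human TB".

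Entry screening has several layers. Section 7.2 excludes people with "Clinical or radiographic features of active tuberculosis", the case record form in Appendix 11 asks the symptom questions before the TST, and section 5 limits longitudinal follow-up to "Participants with a negative blood transcriptional biomarker and who meet the eligibility criteria for the longitudinal study". Follow-up visits are every 3 months for 2 years, the first at month 3.

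Section 5 then defines the cases: "Participants who develop a positive blood transcriptional biomarker or reach a study end point (Appendix 6) as a surrogate for progressive TB". Anyone who meets this description within the two-year follow-up counts as a progressor; no minimum interval after the TST is set. Section 9.2 analyses them together: "Bioinformatic pathway enrichment analysis of outlier gene expression amongst all progressors will be used to identify common immune correlates of risk". Its second analysis, of co-correlated gene clusters, compares progressors with non-progressors and is not split by time either. Section 9.2 also adds progressors found by linkage to national TB surveillance records, again with no stated interval.

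**The concern.** The primary objective concerns TST responses that go with increased risk of active TB; section 4 words it as responses that increase the risk. That reading needs the response to come before the disease. The stated biomarker performance covers people who become symptomatic within 3 months. Someone with subclinical disease at the TST who would become symptomatic at months 3 to 6 could be negative at entry and positive at the first retest. If that disease altered the TST response, the trait would be a consequence of early TB and would be reported as a correlate of risk.

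The chosen method gives no protection. Section 9.1 prefers outlier analysis because it finds traits present in only a subset of progressors, and claims more than 0.8 power when 5 or more share a trait. A disease trait confined to early converters would have that shape.

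**Working it through.** **Inputs from the protocol.** 400 contacts, 5% progression in 2 years and a powered subset of 5 progressors (section 9.1); 8 follow-up visits, months 3 to 24 (section 5, Appendix 11); a 3-month horizon for the biomarker performance (section 2).

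**The plan's own figure.** 400 × 0.05 = 20 progressors, which reproduces. The power of more than 0.8 comes from a simulation on preliminary data and cannot be recomputed from the text.

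**Month-3 converters among the 20.** The protocol gives no timing of conversions, so the share is assumed. If even over 8 visits, it is 1/8 = 0.125. Otherwise take an exponentially falling hazard with rate k per year, solved so that 40%, 50% or 60% of two-year conversions fall in the first 6 months:

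(1 − exp(−0.5k)) / (1 − exp(−2k)) = 0.40, 0.50 or 0.60, giving k = 0.74, 1.22, 1.74.

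Share by month 3 = (1 − exp(−0.25k)) / (1 − exp(−2k)) = 0.218, 0.288, 0.364.

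The last two columns are binomial with n = 20. The final column assumes that half of month-3 converters had disease at the TST, so it uses half the share.

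| Timing assumed | Share | Month-3 converters | Remaining | P(≥5 month-3 converters) | P(≥5 with disease at TST), if half |
|---|---|---|---|---|---|
| Even over 8 visits | 0.125 | 2.5 | 17.5 | 0.10 | 0.01 |
| 40% by 6 months | 0.218 | 4.4 | 15.6 | 0.45 | 0.06 |
| 50% by 6 months | 0.288 | 5.8 | 14.2 | 0.72 | 0.15 |
| 60% by 6 months | 0.364 | 7.3 | 12.7 | 0.91 | 0.29 |

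If only a quarter had disease at the TST, the last column is at most 0.03. These are upper bounds on a declared disease trait, because at least 5 such people must also share the same outlier.

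**What leaving out month-3 converters costs.** A 5-carrier trait is 5/20 = 25% of all progressors. To keep 5 carriers among those who remain, it must be carried by 5/17.5 = 29% to 5/12.7 = 39%. If 6 of 20 are removed and the trait has nothing to do with timing, 5 × 14/20 = 3.5 carriers are expected to remain. The chance that all 5 remain is C(14,5)/C(20,5) = 2002/15504 = 0.13.

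**The case against.** The strongest reply is that three entry screens are used (biomarker, clinical and radiographic, symptom questions), and a person negative on all three who converts later is exactly the progressor the design seeks. Three months is the horizon of one set of predictive values and not a detection limit; section 2 also says, with no time limit, that blood changes can predate diagnosis. This stands against the stronger reading that the entry test is blind beyond 3 months. It does not close the gap, because the protocol gives no time-bound performance for disease that turns symptomatic later.

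A reader might also infer that section 2 shows early infection alters the TST. It does not. The statement about molecular pathology concerns active disease and supports the TST as a model. Reverse causation is therefore possible but not demonstrated.

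A time-split sensitivity analysis could sit in a statistical analysis plan that is not shown. That is fair for the extra run. The progressor definition without an interval, the pooling and the label as correlates of risk are, however, fixed in this protocol.

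Finally, harm to the genetic work should not be overstated. Early TB cannot cause germline genotype, and section 9.2 plans, where possible, to re-examine the eQTLs in published genome-wide association data. What could be misdirected is the choice of TST responses against which eQTLs are compared.

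**Conclusion.** The point holds in a limited form. As written, the analysis for the primary objective cannot separate a response to early disease from a risk response when a trait is confined to people who convert at the first retest. On the assumed timings there would be about 2.5 to 7 such people among 20 progressors. How many had disease at the TST, and whether that would alter the TST response, cannot be learned from the document.

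It would be tempting to read 0.10 to 0.91 as the chance of a false risk response. It is only the chance of at least 5 month-3 converters. It falls to between 0.01 and 0.29 if half had disease at the TST, before any shared trait is required. It would also be too strong to accept as risk correlates only traits also seen in later converters, since that would relabel genuine traits of rapid progression. The finding limits what may be concluded; it does not invalidate the pooled analysis.

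**What to change.** In section 9.2, keep the pooled analysis as primary and add three things:

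- For each significant outlier gene or cluster, report the time from TST to first positive biomarker, end point or linked TB notification among the progressors who carry it.
- Add a sensitivity run leaving out progressors first positive, or reaching an end point, by the month 3 visit.
- Where a trait is confined to month-3 converters, state that early disease at the TST cannot be excluded as its explanation. Do not withdraw the trait on that ground alone.

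The cost is one more analysis. Appendix 11 already records outcomes by visit, and no added visit or sample is needed. The downside is power: with about 13 to 17 progressors left, failure to reproduce a trait in the restricted run is weak evidence against it, so that run should only qualify the main result.

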9.1. Sample size and statistical power

We will recruit 400 LTBI contacts of active pulmonary TB cases to address the primary objective. This sample size is derived from estimated progression from LTBI to active TB within 2 years of 5%, giving 20 progressors and 380 non-progressors. Progressive disease may be due to a range of different immune responses, and each variation may only be evident in a subset of cases. Therefore, conventional differential gene expression analysis in the TST between groups of progressors and non-progressors, may not identify statistically significant differences. Instead, we will undertake supervised outlier profile analysis to identify gene expression among subsets of progressors, which lies outside the normal range measured in non-progressors. These methods provide robust statistical confidence by incorporating multiple testing corrections³²⁻³⁶, and have been successfully applied to discovery of novel oncogenic pathways^{32,37}. Using preliminary TST transcriptomic data from HIV negative individuals in computational simulations, we estimate >0.8 statistical power in this sample size to detect significant outlier traits among progressors (false discovery rate <0.05) when the outlier trait is shared by 5 or more progressors (Figure 2A). In order to identify eQTLs of TST transcriptomic data, we estimate that a sample size of 1000 is required to give >90% power to detect statistically significant correlations ($p < 10^{-8}$) for allelic frequencies $\geq 5\%$ depending on the correlation coefficients, as a composite measure of effect size and variance⁶¹. Finally, from our pilot data, we estimate that 15% of these individuals will express the blood transcriptional biomarker at time of recruitment to the study. Of these estimated 150 participants, 80 will be recruited to the LTBI treatment sub-study. Conservatively assuming that only 25% of patients decline LTBI therapy, a sample size of 68 participants will provide 80% power to detect a difference of 0.8 standard deviations (SDs) in signature scores between those who accept and decline treatment at each time point. This calculation assumes similar standard deviations among individuals in both groups. We have estimated 0.8SDs as the minimum difference in signature scores that is likely to be of clinical significance (based on the difference in mean scores between IGRA-positive and IGRA-negative TB case-contacts in our pilot data. To allow for losses to follow-up, 80 participants will be recruited.

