Appendix 6: Study end points

Participation in the study will end with any one of the following events and participants will go on to have routine clinical assessments to evaluate the need for LTBI or active TB treatment.

1. 2 year follow up completed
2. Changes in chest radiography (airspace shadowing or lymphadenopathy) consistent with progressive/active TB with at least one yes answer in the symptom questionnaire.
3. Two yes answers in the symptom questionnaire.

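### Section 9.2 adds surveillance-linked TB cases among migrants to surrogate-defined progressors among contacts, so case status is mixed with outcome definition and recruitment source

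*Protocol*

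**What the plan says.** Section 9.1 ties the primary objective to one cohort: "We will recruit 400 LTBI contacts of active pulmonary TB cases to address the primary objective". Its expected size rests on "estimated progression from LTBI to active TB within 2 years of 5%, giving 20 progressors and 380 non-progressors".

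Section 5 (Study schedule) says how members of that cohort are classified. Those who develop a positive blood biomarker "or reach a study end point (Appendix 6) as a surrogate for progressive TB before 2 years, will be identified as progressors". One Appendix 6 end point is simply "Two yes answers in the symptom questionnaire"; another is a radiographic change with at least one symptom. For the other group, "Participants who complete 2 years follow up will be identified as non-progressors".

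The other 600 participants have a different origin: "The additional individuals for the cross-sectional study will be recruited from the Public Health New migrant screening program referrals to LTBI clinics". Being a contact of a pulmonary case is an inclusion criterion for the longitudinal study only (section 7.1).

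Section 9.2 then states that data from cross-sectional participants, and from longitudinal participants who withdraw or are lost before 2 years, "will be included by identifying any progressors amongst these groups by linkage to national TB surveillance records". It gives no time window for a linked case and does not say who the comparators are. It runs the pathway analysis on all progressors together, and compares gene clusters between progressors and non-progressors without reference to source.

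**The concern.** Two problems come from the same sentence.

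- **Outcome.** In contacts, a progressor has a biomarker, symptom or radiographic event looked for every 3 months. In linked participants, a progressor has a national TB surveillance record, at any time. These are different states under one label.
- **Source.** Only longitudinal contacts can meet the definition of a non-progressor, while linked progressors include migrants. Any expression difference between migrants and contacts that has nothing to do with progression (for example from ancestry, BCG history or recency of infection, if these affect the TST) then leaks into the progressor v non-progressor contrast.

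The comparison affected is the one that serves the primary objective. Section 9.2 also carries its results forward, by asking whether eQTLs relate to the immune variation found to correlate with progression. A source artefact could therefore pass into the search for susceptibility loci.

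**Working it through.** **1. The plan's own figure.** 400 x 0.05 = 20 progressors and 400 x 0.95 = 380 non-progressors. This reproduces section 9.1. The power above 0.8 comes from the sponsor's simulations on preliminary data and cannot be recomputed from the document.

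**2. Are the two outcomes interchangeable?** Section 9.1 expects 15% of participants to be biomarker-positive at recruitment, against a 2-year TB risk of 5%. Even if every case arose among positives, at most 5/15 = 33% of them would progress. This is only indicative: the 15% refers to all 1000 at baseline, the 5% to contacts over 2 years.

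**3. Time at risk.** Recruitment runs over four years (section 4) in a five-year study (summary information). The last cross-sectional recruits have about 5 - 4 = 1 year of linkage by study end and the earliest about 5, against 2 years in contacts.

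**4. Size of the source shift.** Let D be the mean expression difference between migrants and contacts, with no true progression effect, and let m migrant cases join 20 contact progressors, with 380 contacts as controls. The expected spurious difference is

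m / (20 + m) x D.

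The protocol gives no TB risk for the 600 migrants. Assuming m = 2 to 6 (0.3% to 1% of 600):

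- m = 2: 2/22 = 0.09 D
- m = 6: 6/26 = 0.23 D

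**5. False-positive rate of one cluster comparison.** Two-sample t-test, two-sided 5%, normal data with equal variance, no multiplicity correction, 20,000 simulated trials per cell. D is assumed, as the protocol gives no value.

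| Migrant cases m | Share of progressors | D = 0 | D = 0.5 SD | D = 1 SD |
|---|---|---|---|---|
| 2 | 0.09 | 5% | 5% | 7% |
| 6 | 0.23 | 5% | 9% | 20% |
| 12 | 0.38 | 5% | 17% | 52% |
| 30 | 0.60 | 5% | 51% | 98% |

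The last two rows show the trend only. Thirty cases would mean applying the contacts' 5% risk to the migrants, which the protocol does not do.

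**6. Outlier analysis.** Section 9.1 seeks gene expression outside the range of non-progressors, with power stated at "false discovery rate <0.05) when the outlier trait is shared by 5 or more progressors". Under an assumed rule (above the third quartile plus one interquartile range of controls), 5 or more outlying progressors occurred in at most about 1.2% of runs for m = 2 to 6 and D up to 1 SD. The protocol does not fix the rule, so this neither establishes nor excludes a material effect.

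**The case against.** The strongest reply is that the protocol already centres the primary objective on the 400 contacts (sections 4 and 9.1), that linkage is a sensible way to recover missed cases, and that stratification and adjustment commonly belong in an SAP. The case record form collects referral reason, country of birth, ethnicity, BCG and whether LTBI treatment was started, so the data for adjustment largely exist. Much of this stands. Drop-outs are themselves contacts, so the source problem does not touch them, and linking them is sound apart from the change of outcome definition. What does not stand is that nothing needs changing in the protocol: the two definitions, the missing window and the inclusion of cross-sectional cases are stated there.

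Three stronger readings are tempting but not supported.

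- **Migrants without TB counted as non-progressors.** With 2 to 6 migrant cases, contacts would then be 20/22 = 91% to 20/26 = 77% of progressors, but 380/978 = 39% to 380/974 = 39% of non-progressors, a shift of 0.52 to 0.38 D. Section 5 reserves the non-progressor label for people completing 2 years of follow-up, and section 9.2 speaks only of identifying progressors, so the text does not clearly say this.
- **LTBI treatment as a confounder of TST expression.** Section 5 schedules the skin tests and biopsies before treatment is offered, so treatment cannot alter what is measured. It can only avert or hide progression in people not followed under deferral. The 40-60% acceptance in section 4 is given for the treatment sub-study, not for all 600.
- **Every gene that differs by source would appear as a risk correlate.** The table does not show that: at 2 to 6 migrant cases the inflation is modest unless D is large.

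**Conclusion.** The concern holds in limited form. As written, section 9.2 mixes a surveillance-recorded outcome with a surrogate one and sets migrant cases against contact controls. The direction of the defect follows from the text; its size does not. With 2 to 6 migrant cases the spurious difference is 0.09 to 0.23 D, and the cluster-test error is roughly 5-9% at D = 0.5 SD and 7-20% at D = 1 SD. These figures rest on the assumed case count and D, on 20 contact progressors, and on an uncorrected t-test. The error grows with more migrant cases and stays nominal if expression does not differ by source. No effect on the outlier analysis has been demonstrated. The change is worth making because it protects the primary comparison at little cost.

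**What to change.** Amend section 9.2 to state that:

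1. The primary progressor v non-progressor contrast is made within the longitudinal contact cohort. Surveillance linkage is applied to all its members, completers as well as drop-outs, over the same 2-year window.
2. Linked progressors from the cross-sectional group are analysed separately, or in a pooled analysis stratified by recruitment source. Their comparators are non-progressors from the same source, the common outcome is notified active TB within 2 years of recruitment, and LTBI treatment is taken into account.

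**Cost.** This is mainly a change of wording. The case record form has a yes/no item for starting LTBI treatment but no date, so one date field would help with the second step. A 2-year window for late cross-sectional recruits also needs linkage beyond the current end of study, or censoring at that date. No extra visits or samples are needed, and the 20 v 380 split behind section 9.1 is kept. The downside is that a few migrant progressors leave the primary analysis.
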